5.1 INCLUSION CRITERIA

Participants are eligible to be included in the study only if all of the following criteria apply:

Age

- I 01. Participant must be between 12 to 65 years of age (inclusive), at the time of signing the informed consent.

Type of participant and disease characteristics

Atopic dermatitis patients and healthy volunteers:

- I 02. Male or female patients.
- I 03. Patients with AD diagnosis according to Hanifin and Rajka criteria at least 1 year before screening. (AD patients only)
- I 04. Investigator Global Assessment (IGA) score of ≥ 3 at screening (on the 0-4 scale). (AD patients only)
- I 05. Patients with moderate to severe atopic dermatitis that are eligible to be treated with dupilumab according to product monograph. (AD patients only)
- I 06. Patients with AD must have active lesions on the upper limbs or lower limbs, with severity for lesion erythema or edema/papulation ≥ 2 at screening on the 0-3 scale of the ISS. (AD patients only)
- I 07. Participants should have a non-lesional (normal looking) skin area 4 cm from the edge of the lesional area. If unable to identify non-lesional skin 4 cm from the lesional area, it is acceptable to identify normal looking skin as close to the lesion as possible. (AD patients only)
- I 08. Willing to refrain from applying any topical medication products on the target assessment areas (including lesional and non-lesional) throughout the study until the EoT visit unless necessary to alleviate intolerable symptoms.

- I 09. Willing to refrain taking showers or soaking in a bathtub with soaps and body washes within 6 hours before TEWL assessments.
- I 10. Willing to NOT apply any moisturizers to the areas of the skin that are targeted assessment areas (lesional and non-lesional) during the entire study from Day -7 to the EoT visit.
- I 11. Willing and able to comply with all clinic visits and study-related procedures.

Healthy volunteers only:

- I 12. Age and gender matched to a selected AD patient by study site. Adolescents aged 12 to 17 years will be matched by post puberty status, and adults aged 18 to 65 years will be matched by age as close as possible within 10 years of age.
- I 13. No current dermatologic or systemic condition that could interfere with the assessments.

Weight

Not applicable.

Sex

- I 14. Male or Female

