8.2.11 Quality of Sleep NRS

Quality of Sleep NRS to collect information on patient-reported quality of sleep. Numerical rating scale range is from 0 (“worst possible sleep”) to 10 (“best possible sleep”).

Patients will complete the rating scale daily from Day-7 until Day 29, and then until Day 113 (EoT) at the week before the visits as indicated at [Section 1.3](#).

The Quality of Sleep NRS will be provided in the study reference manual.

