9.4.4.2 Baseline efficacy parameters

Baseline is defined as the last available and evaluable value before and closest to the first dose of the IMP: ie, at D1 (V02, W0), for patients and as the last available and evaluable value at D1 (V02, W0) for healthy volunteers. For TEWL data, the average of the values of the 3 spots within each predefined skin area will be used as baseline, unless a large difference between the spots is observed.

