
Change (percent and absolute) from baseline in EASI over time
 
Change (percent and absolute) from baseline in SCORAD over time
 
Change (percent and absolute) from baseline in ISS over time
 
Change (percent and absolute) from baseline in POEM over time
 
Change (percent and absolute) from baseline in DLQI in patients 18 years of age and CDLQI in patients ≥ 12 and < 18 years of age over time
 
Change (percent and absolute) from baseline in peak pruritus NRS over time
 
Change (percent and absolute) from baseline in quality of sleep NRS over time
 
Change (percent and absolute) from baseline in photograph outputs (eg, severity score) obtained from skin imaging over time
	
EASI, SCORAD, POEM, DLQI/CDLQI, peak pruritus NRS, and quality of sleep NRS, photograph outputs:
 
 • Raw data and change from baseline; ie, absolute and percentage changes, will be summarized with descriptive statistics (such as mean, median, SD, minimum, and maximum) by time points based on patients from mITT population. • Mean plots (mean \pm SEM) on raw data and absolute change from baseline over time for patients' cohort will be produced. 
ISS:
 
 • Number and percentage of patients by severity will be reported by time points based on the patients from mITT population. • Barplot (percentages of patients by severity grade) over time for patients' cohort will be produced.

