1.2 MODIFICATIONS FROM THE STATISTICAL SECTION OF THE PROTOCOL

This section describes the modifications and additional statistical analyses from the protocol.

Due to unbalance between adults and adolescents atopic dermatitis (AD) patients, analyses based on age group (adult/adolescent) will only be performed for adverse event (AE) data reporting.

The study objectives are exploratory. Sample size was not based on power requirements. No multiplicity correction will be used for the tests performed as part of the statistical analyses.

Analysis population

Any participant with major deviation impacting assessment of efficacy data (except for deviations concerning AD related prohibited therapy administration) will be excluded for the modified-Intent-to-treat (mITT) population.

Demographic and medication data

Descriptive statistics for disease duration since AD diagnostic will be provided by cohort and age group (adults/adolescents).

Medications (including rescue medications) administered during the follow-up period will be summarized, in addition to previous and concomitant medications.

Efficacy analysis

Change from baseline in TEWL data is defined as change versus Day 1 TEWL data at matched number of STS samples (eg, TEWL after 5 STS at Week 16 will be compared to TEWL after 5 STS at Day 1).

Individual Signs Score (ISS) questionnaire was not done as planned per protocol. Instead, to assess lesion severity locally, Quantificare evaluation data will be used. Global Individual Signs Score (GISS) was evaluated during the study. Both Quantificare data and GISS data will be analyzed using descriptive statistics for raw data, absolute and percent by timepoints. For AD patients, on mITT population, correlation with TEWL data will be evaluated. Scatterplots will be provided to visualize the form of the relationship and Spearman's rank correlation coefficient as well as p-values at specific timepoints (Baseline, Week 8 and Week 16) will be provided.

Adverse event data

All summary of AEs will be provided by cohort and age group.

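### Percent change from baseline is planned for the quality of sleep NRS, where 0 is the worst score, so that one summary has no value at a baseline of 0 and becomes very large just above it

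*Protocol*

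**What the plan says.** Protocol Section 9.4.7.1, Table 4, includes among the tertiary endpoints "Change (percent and absolute) from baseline in quality of sleep NRS over time". The method for the group of scales containing the sleep NRS is: "Raw data and change from baseline; ie, absolute and percentage changes, will be summarized with descriptive statistics", with mean, median, SD, minimum and maximum as examples. Mean plots "on raw data and absolute change from baseline over time for patients' cohort will be produced", so percent change appears only in the tables.

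Section 8.2.11 sets the scale: "Numerical rating scale range is from 0 (“worst possible sleep”) to 10 (“best possible sleep". Section 9.4.4.2 sets the reference value: "Baseline is defined as the last available and evaluable value before and closest to the first dose of the IMP". Diary scores are collected daily in the week before Day 1 (Section 1.3, footnote g), but no averaging over that week is stated.

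Table 4 also correlates percent change in TEWL with the corresponding change in each clinical and patient-reported measure at Weeks 8 and 16. It uses Pearson's coefficient for the sleep NRS and does not say whether the sleep change is percent or absolute.

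For the lesion signs, Table 4 names percent and absolute change in ISS as an endpoint but gives counts by severity grade as the method. SAP Section 1.2 says: "Both Quantificare data and GISS data will be analyzed using descriptive statistics for raw data, absolute and percent by timepoints".

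**The concern.** Table 4 applies one method to scales that run in opposite directions. On EASI, SCORAD, POEM, DLQI/CDLQI and the itch NRS, 0 is the best score. A small baseline there belongs to a mildly affected patient, and improvement cannot pass -100%. On the sleep NRS the small baselines belong to the worst sleepers, who have the most room to improve, and the ratio has no comparable ceiling: a rise from 1 to 10 is +900%. A baseline of 0 gives no value at all, so those who drop out of the percent summary are not a random subset.

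No eligibility criterion sets a minimum sleep score, so 0 can occur. Neither document reverses the scale or says what to do with a zero. With about 20 patients, one or two low baselines can set the mean and SD of the percent change. If percent change also enters the Pearson correlation with TEWL, the same patients can dominate the coefficient.

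**Working it through.** **Inputs.** Scale 0 to 10 with 0 worst (Section 8.2.11). Baseline is a single value (Section 9.4.4.2). Twenty evaluable patients (Section 9.2); the plan's enrolment figure reproduces, 20 / (1 - 0.15) = 23.5, rounded up to 24. The plan gives no figure for the sleep score, so every baseline distribution below is an assumption.

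**Step 1: the ratio.** Percent change = 100 × (follow-up - baseline) / baseline. For a 3-point gain:

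| Baseline | Absolute change | Percent change |
|---|---|---|
| 0 | +3 | undefined |
| 1 | +3 | 300/1 = +300% |
| 4 | +3 | 300/4 = +75% |
| 5 | +3 | 300/5 = +60% |
| 7 | +3 | 300/7 = +43% |

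A 7-day mean baseline would make exact zeros rarer but would not cure this. A baseline of 1/7 rising to 8 gives 100 × (8 - 1/7) / (1/7) = +5500%.

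**Step 2: effect on a group summary.** Let 20 patients all gain 3 points.
- All start at 5: mean percent change 60%.
- One starts at 1 instead: (19 × 60 + 300) / 20 = 72%. The SD goes from 0 to 54; the median stays at 60%.
- Seventeen start at 5, two at 1, one at 0: (17 × 60 + 2 × 300) / 19 = 85% on 19 patients. The median is 60%, and the mean absolute change is 3.0 on all 20.

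**Step 3: how often a zero would occur.** Take baseline as Normal(m, s), rounded and clipped to 0-10. Then p0 = Φ((0.5 - m)/s), and the chance of at least one zero in 20 is 1 - (1 - p0)^20. Example: m = 4, s = 2 gives p0 = Φ(-1.75) = 0.040 and 1 - 0.960^20 = 56%. For the percent changes I simulated 100,000 trials of 20 patients per row, with gain Normal(2, 1.5) and follow-up capped at 10. The last column is the typical within-trial difference between mean and median percent change.

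| Mean / SD (assumed) | At least one 0 | At least one 0 or 1 | Typical mean percent change | Mean minus median (points) |
|---|---|---|---|---|
| 4.5 / 2.3 | 57% | 87% | 54% | 12.6 |
| 4 / 2 | 56% | 89% | 61% | 13.1 |
| 4.5 / 1.8 | 23% | 62% | 52% | 9.0 |
| 5 / 2 | 22% | 56% | 46% | 8.5 |
| 5.5 / 2 | 12% | 37% | 40% | 6.9 |
| 6 / 2 | 6% | 22% | 35% | 5.7 |

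Pairing the extremes of the same ranges widens this: 4 / 2.3 gives 73% and 14.9 points, and 6 / 1.8 gives 2% and 4.5 points. The chance of a zero depends heavily on the assumption. The upward pull on the mean is present in every row.

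**Step 4: the lesion signs.** Section 8.2.5 grades each sign 0 to 3. Inclusion criterion I 06 asks for active lesions "with severity for lesion erythema or edema/papulation" of at least 2 at screening, so one of the two signs may be 0. A sign at 0 has no percent change. A summed score would rarely be 0 in patients who meet I 06 and have IGA of at least 3. The SAP does not say whether GISS is analysed by sign or as a total.

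**The case against.** The strongest reply is that the plan already contains what is needed. Raw scores and absolute change are summarized beside percent change, the median beside the mean, and the plots use raw and absolute values only. That stands. A reader might infer that the worst sleepers disappear from the sleep results, or that a sign worsening from 0 goes unseen. The documents do not support either: both remain in the raw and absolute summaries.

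A reader might also infer that percent change in sleep is correlated with TEWL. Table 4 specifies percent for TEWL but not for the other measures, so this is an ambiguity and not a stated plan. Scatterplots are planned too and would expose an extreme point.

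The GISS extension is weaker still. Percent change in ISS was already a protocol endpoint, and Section 8.2.5 treats ISS and GISS as names for one scale, so the SAP changed the summary method and not the endpoint. Its sentence says percent without the word change. I 06 is a screening criterion for the target lesion and only indirect evidence about baseline GISS. The SAP uses Spearman's coefficient for GISS, which limits extreme values, though not undefined ones.

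Finally, nothing shows that a low sleep score marks the most severe dermatitis, so the affected patients are the worst sleepers and not necessarily the sickest. What survives is narrow: a pre-specified statistic that can be undefined, on a scale where the loss is informative, with no rule for it.

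**Conclusion.** The point holds as a minor one. Percent change is a poor summary for a scale whose worst score is 0. Followed as written, the plan drops any patient with a baseline of 0 from that row and inflates those just above. The ratio in Step 1 needs no assumption. The frequency does: about 6% to 57% for at least one zero among 20 patients over six illustrative distributions, and 2% to 73% at the extreme pairings. The excess of mean over median percent change is about 6 to 13 points, or 5 to 15 at the extremes, and also rests on the assumed gain.

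The effect on the TEWL correlation is conditional on percent change being used there, and the GISS problem on signs being analysed one by one. The endpoint is tertiary, in a study with no predefined hypothesis testing (Section 9.1). No primary, secondary or safety result is touched.

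**What to change.** Before database lock, in the SAP:

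1. Drop percent change for the quality of sleep NRS and report raw scores and absolute change.
2. State that absolute change in the sleep NRS enters the correlation with percent change in TEWL at Weeks 8 and 16.
3. Label each table of patient-reported outcomes with the direction of the scale.
4. Say whether GISS is analysed by sign or as a total. If by sign, keep Table 4's counts by severity grade and limit percent change to a total score with a baseline above 0.

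Dividing the change by (10 minus baseline) is not a clean substitute, because it is undefined at a baseline of 10.

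The cost is wording. One exploratory percent-change summary is lost; absolute change is already planned and no new data are needed.

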
 Explore the association of skin barrier function measured by TEWL with disease severity assessed by standard AD severity assessments (Eczema Area and Severity Index (EASI), SCORing Atopic Dermatitis (SCORAD), local lesion severity on target lesion), patient reported outcomes (PRO) (Patient Oriented Eczema Measure (POEM), Dermatology Life Quality Index (DLQI) / Children Dermatology Life Questionnaire Index (CDLQI), peak pruritus Numerical Rating Scale (NRS), and quality of sleep NRS), standardized photos, and the biomarker profiles of lipidomics, proteomics, and transcriptomics assessed in the STS sample. 	
 Change (percent and absolute) from baseline in EASI over time. Change (percent and absolute) from baseline in SCORAD over time. Change (percent and absolute) from baseline in Individual Signs Score (ISS) for target lesion over time. Change (percent and absolute) from baseline in PRO (POEM) over time. Change (percent and absolute) from baseline in PRO of DLQI in patients 18 years of age and older / CDLQI in patients ≥ 12 and < 18 years of age over time. Change (percent and absolute) from baseline in PRO of peak pruritus NRS over time. Change (percent and absolute) from baseline in PRO of quality of sleep NRS over time. Change (percent and absolute) from baseline in photograph outputs (eg, severity score) obtained from skin imaging over time. Correlation between baseline values of TEWL before STS and TEWL AUC in lesional and non-lesional skin of AD patients with the following baseline measures: 
 Local target lesion erythema and edema/papulation; ISS EASI, SCORAD

Objectives	Endpoints

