Based on the aforementioned potential benefits to patients participating in LPS15991, the Sponsor assessment is that the benefit-risk remains favorable for patient to participate in this trial. The proposed study will evaluate the effect of dupilumab on the skin barrier in adult and adolescent population with moderate-to-severe AD. The efficacy and safety of dupilumab were confirmed based on data that included in pivotal Phase 3 trials in which dupilumab were used alone or in combination with topical corticosteroids (TCS) and compared to placebo or TCS alone in patients with moderate to severe AD. In the trials, patients treated with dupilumab alone or in combined with TCS experienced significant improvements in overall disease severity, skin clearance and quality of life. Therefore, the operation of LPS15991 will allow enrolled AD patients the opportunity to receive a therapy which may provide benefit in improving their skin barrier function, overall disease severity, and quality of life. Participants in the healthy volunteers' cohort will not benefit directly from participation in this study, other than the nominal reimbursements provided for completing study procedures and visits. However, the results obtained from healthy volunteers in comparison with AD patients will allow the Sponsor to better understand the immune, epidermal, and barrier defects observed in AD patients. The Sponsor also recognizes that the "Coronavirus Disease 2019" (COVID-19) pandemic may have an impact on the conduct of clinical trials. The Sponsor will monitor the situation closely and ensure the integrity of the trial conduct and data (see [Section 8](#)).

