6.3 MEASURES TO MINIMIZE BIAS

The study is open label study without a treatment control group in patients. To control bias, the following measures are taken:

- Age-, gender-, targeted lesion area-, and study site-matched healthy volunteers will serve as a reference comparator cohort for interpreting study results.
- PROs will be collected by electronic data capture.
- Efficacy data (TEWL) will be measured by the same device model.
- Biomarker data (lipidomics, proteomics, and transcriptomics) will be measured by an experienced, central laboratory.
- Study is limited to 2 very experienced study centers
- One central laboratory for lipidomics, proteomics and transcriptomics analyses to reduce skin barrier assessment variabilities.
- Standardized study assessment procedures, including TEWL and STS skin barrier function
- Standardized photography for targeted lesional and non-lesional areas, and clinical disease severity and patient reported outcome evaluations.
- Reason for screen failures (if any) will be documented.

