8.2 EFFICACY ASSESSMENTS

8.2.1 Transepidermal water loss assessment and skin tape stripping

8.2.1.1 Transepidermal water loss assessment

Transepidermal water loss is a skin barrier function test that measures perspiration or water loss through the skin. Transepidermal water loss is generally higher in AD skin compared to normal skin as the barrier is disrupted allowing water to evaporate more readily. If the barrier improves with dupilumab treatment, TEWL would be expected to decrease.

TEWL assessment will be conducted in a quiet environment with temperature and humidity being documented. TEWL measurements will be conducted in the same room throughout the study where possible. Subjects will be acclimated to the room for a minimum of 20 minutes prior to TEWL measurements. Room temperature will be set to be within 19.0°C to 23.0°C. Humidity will be set to be below 60% as the maximum allowed humidity. To further control TEWL readout, moisturizers will be standardized for all study participants starting from Day -7 until Day 113 (Week 16). The first TEWL assessment at each visit will be conducted at each of the three spots in predefined lesional and non-lesional areas respectively. After start of STS all subsequent TEWL assessments at each visit will be done on the single lesional and non-lesional spot respectively at which the STS is performed (see also [Figure 3](#)).

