8.2.3 Questionnaires and patient reported outcome assessments (PROs)

Questionnaires and patient-reported assessments will only be conducted in AD patients. Patient reported outcomes will be collected in an appropriate form, for which the respective device, diary and/or instruction is handed out to the patient at the screening (or baseline) visit. The electronic diary will be only used by the subset of patients who speak fluently the language in which adequate translations (ie, validated translations where applicable) are available. These Patient-Reported Outcome (PRO) questionnaires and NRS should be completed by the patients before the TEWL assessment at each visit and in a quiet place. The questionnaires should be completed by the patients themselves, independently from their physician, the study nurse or any other medical personnel and without any help from friends or relatives.

Patients will bring the diary to the site at each visit. Diary will be reviewed for any questionnaires omission and dispensed back to patients at each visit.

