9.2 SAMPLE SIZE DETERMINATION

Sample size for this exploratory study was based on medical/clinical judgement and is consistent with the sample size from similar studies in the literature (1). No formal sample size calculation was performed. TEWL data collected in similar settings as planned for this study were not available: ie, TEWL values after 5 skin tape strips, and pre- and post-dupilumab treatment are unknown.

Allowing for drop-out rate of 15%, a total of approximately 24 patients with moderate to severe AD will be enrolled to achieve 20 evaluable patients: ie, patients with no major or critical deviations related to IMP and/or TEWL measurements, for whom the TEWL data for primary analysis: ie, TEWL at baseline and Week16, are considered sufficient and interpretable. An approximately equal number of age, gender, location of targeted lesion area and site matched healthy volunteers serving as a reference comparator cohort will be enrolled. Drop-out rate in healthy volunteers is expected to be zero. Any drop-out healthy volunteer for whom the matched patient is considered as evaluable will not be replaced.

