
Correlation between baseline values of TEWL before STS and TEWL AUC in lesional and non-lesional skin of AD patients with the following baseline measures:
 
 • Local target lesion erythema and edema/papulations; ISS • EASI, SCORAD • POEM, DLQI, CDLQI, peak pruritus NRS, and quality of sleep NRS • Lipidomics in STS (ratio of EOS CER to NS CER) • FLG breakdown products of UCA and PCA concentrations in STS • Key components of skin proteomics in STS (expression of proteins associated with skin barrier function) • Key components of gene expression from transcriptomics • Image-derived severity score in targeted lesional skin 	
Scatterplot to visualize the form of the relationship between variables will be produced for patients' cohort at specific time points: ie, baseline, Week 8 and Week 16, based on the mITT population.
 
Pearson correlation will be assessed at each defined time points for EASI, SCORAD, POEM, DLQI/CDLQI, peak pruritus NRS, quality of sleep NRS, and photograph outputs. Pearson correlation coefficient and p-value will be reported.
 
Spearman's rank correlation will be assessed at each defined time points for ISS. Spearman correlation coefficient and p-value will be reported.
 
As exploratory analysis repeated measures correlation method might be used to assess the overall correlation pooling data from baseline, Week 8 and Week 16 (34).

Endpoint	Statistical Analysis Methods
Correlation between percent change from baseline in TEWL before STS and TEWL AUC in lesional and non-lesional skin of AD patients at Week 8 and Week 16 with corresponding change from baseline in the following measures:	
• Local target lesion erythema and edema/papulations; ISS• EASI, SCORAD• POEM, DLQI, CDLQI, peak pruritus NRS, and quality of sleep NRS• Lipidomics in STS (ratio of EOS CER to NS CER)• FLG breakdown products of UCA and PCA concentrations in STS• Key components of skin proteomics in STS (expression of proteins associated with skin barrier function)• Key components of gene expression from transcriptomics• Image-derived severity score in targeted lesional skin

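### The optional pooled repeated measures correlation states no visit term; in its standard form it would mix the shared on-treatment course into the association between TEWL and severity

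*Protocol*

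**What the plan says.** One tertiary objective in Protocol Section 1.1 is to "Explore the association of skin barrier function measured by TEWL with disease severity assessed by standard AD severity assessments", together with patient-reported outcomes, images and biomarkers. Table 4 in Section 9.4.7.1 serves it in three ways:

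- Scatterplots and correlations "at specific time points: ie, baseline, Week 8 and Week 16, based on the mITT population". Pearson or Spearman coefficients are reported with p-values.
- Correlations of percent change in TEWL with change in the partner measure at Weeks 8 and 16.
- An optional exploratory addition: a "repeated measures correlation method might be used to assess the overall correlation pooling data from baseline, Week 8 and Week 16". The text gives a literature reference but no model terms, and it does not say whether a p-value will be reported.

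The SAP refers back to Protocol Section 9 for technique (SAP 1.1). Its own correlation text (SAP 1.2) covers only Spearman coefficients at single visits for the GISS and image data. It does not mention the pooled method or a visit term, and it applies no multiplicity correction.

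On design, Protocol Section 6.3 states: "The study is open label study without a treatment control group in patients". Healthy volunteers cannot supply an untreated course for the patient-reported outcomes: "Questionnaires and patient-reported assessments will only be conducted in AD patients" (Section 8.2.3).

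**The concern.** Repeated measures correlation in its usual form fits patient as a factor with one common slope. That removes differences in level between patients but leaves the average movement from visit to visit. Here one pooled visit precedes treatment and two are on treatment, and all patients follow the same schedule.

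The protocol expects movement in both members of most pairs. On TEWL, Section 8.2.1.1 says: "If the barrier improves with dupilumab treatment, TEWL would be expected to decrease". On the clinical side, Section 2.3.3 reports that patients in the pivotal trials "experienced significant improvements in overall disease severity, skin clearance and quality of life".

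The pooled coefficient then answers two questions at once: do both measures improve on treatment, and do patients whose barrier improves more also improve more clinically? Readers of an association objective will mostly want the second. The pooled coefficient also has the most degrees of freedom of the planned correlations, so it could look like the strongest evidence while owing much of its size to the first.

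**Working it through.** **The plan's own figure.** No figure is stated for the correlation analysis. The one design number that can be reproduced is enrolment. Section 9.2 plans "a total of approximately 24 patients with moderate to severe AD will be enrolled to achieve 20 evaluable patients" with 15% drop-out: 20/0.85 = 23.5, rounded up to 24. It reproduces. I use n = 20, with n = 24 as a check.

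**Inputs**

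- From Table 4: three visits (baseline, Week 8, Week 16), AD patients only.
- Assumed, because Section 9.2 gives no SD or effect size: each measure has within-patient residual SD 1, and both shift by D residual SDs. Two time profiles are used: full shift by Week 8 (0, 1, 1), and 80% of the shift by Week 8 (0, 0.8, 1).
- Assumed true residual correlation: 0, meaning no relation once visit means are removed.

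**Formula.** After centring on patient means, the expected within-patient residual sum of squares per patient is 2 (three visits minus one mean). The common course adds D²S, where S is the sum of squares of the centred profile. The same D²S enters the cross-product, so approximately

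r = D²S / (2 + D²S).

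- Profile (0, 1, 1): mean 2/3, S = 4/9 + 1/9 + 1/9 = 2/3.
- Profile (0, 0.8, 1): mean 0.6, S = 0.36 + 0.04 + 0.16 = 0.56.

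Example, D = 1.5: 2.25 × 0.56 = 1.26, and 1.26/3.26 = 0.39. With S = 2/3: 1.5/3.5 = 0.43.

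**Simulation.** n = 20, two-sided 5% test, df = 3n − n − 1 = 39 without visit and 37 with it. There were 10,000 trials per setting for the 80% profile. The full-by-Week-8 profile was simulated twice (4,000 trials per setting in one run), and both results are shown.

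| Shift D | r, 80% by Week 8 | p<0.05 | r, full by Week 8 | p<0.05 |
|---|---|---|---|---|
| 0 | 0.00 | 4.9% | – | – |
| 0.5 | 0.07 | 7.1% | 0.08 (formula) | not run |
| 1 | 0.22 | 27.6% | 0.25 | 35–36% |
| 1.5 | 0.39 | 74.4% | 0.43 | 84–85% |
| 2 | 0.53 | 97.6% | 0.57 | 99% |
| 3 | 0.72 | 100% | 0.75 | 100% |

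With n = 24 and the 80% profile, rejection is 33.0%, 82.1% and 99.3% at D = 1, 1.5 and 2.

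**With visit in the model.** Mean r is about 0.00 and rejection is 4.7% to 5.5% in every setting.

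**Direction.** If only one measure shifts (2 SD and 0), r is 0.00 and rejection 5.1%. If one falls and the other rises by 1.5 SD, r is −0.39 and rejection 75.0%. The second case fits the quality of sleep NRS, where higher is better (Section 8.2.11).

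**Is real signal kept?** With a true residual correlation of 0.30 and D = 1.5, the unadjusted expectation is (1.26 + 0.30 × 2)/3.26 = 0.57, and simulation also gives 0.57. The visit-adjusted estimate is 0.30.

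**The planned companions.** Correlations at Week 16, and of change with change at Week 16, compare patients with one another at one time, so a common shift drops out. With true correlation 0, simulated r is about 0 and rejection 4.4% to 5.4%. The simulation used absolute change in both measures, whereas the plan uses percent change for TEWL.

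**The case against.** Several counter-arguments have weight.

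- **It is optional.** The sentence says the method might be used. The pooled coefficient is not a listed endpoint, and the SAP does not take it up. A reader might infer that the plan commits to an analysis that will return a spurious significant result. The documents do not support that: nothing binds the sponsor to run it, and no p-value is promised for it. The rejection rates apply only if one is reported.
- **The missing visit term is inferred.** The text lists no model terms, and the cited method paper was not available to consult. What can be said is that no visit term is stated and that the method's standard form has none.
- **The common course may be of interest.** Two measures that both fall in every patient do move together within patients, so it would be wrong to call them unrelated within patients. Section 4.2 speaks of barrier kinetics and therapeutic response, and describing co-movement is a legitimate aim. This supports keeping an unadjusted coefficient if it is labelled, but calling it an overall correlation does not tell the reader what it contains.
- **Not every pair is affected.** A reader might infer that any two measures that both fall will give a large correlation. The size depends on both shifts and is trivial at 0.5 SD.
- **Unaffected analyses are already planned.** This limits the damage, but the pooled figure would appear beside them and could outshine them.

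**Conclusion.** The point holds for the pooled analysis if it is run in its standard form. Two responding measures would then correlate through the shared on-treatment course even if they are unrelated once common visit means are removed. The effect is minor at a shift of 0.5 within-patient SDs and substantial from about 1.5 SDs.

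The shift sizes, time profiles and independent residuals are assumptions. The documents give no effect size for TEWL in lesional or non-lesional skin, or for the severity measures.

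The consequence is for interpreting a tertiary, exploratory objective. The primary endpoint is untouched. The correction is worth making before analysis because it is specific, uses data already collected, and recovers a real association where one exists.

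**What to change.** In Table 4 or the SAP, state that if the pooled correlation is run, the model includes categorical visit as well as patient, with degrees of freedom reduced by 2 (39 to 37 at n = 20 with complete data). Base statements about association on that coefficient and on the planned change-versus-change correlations. If the unadjusted coefficient is also shown, label it as including the common on-treatment time course.

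The cost is one extra model term and no new data. Reported coefficients will usually be smaller in size, and fewer will reach 0.05. With a true residual correlation of 0.30 and n = 20, the adjusted test rejects in about 47% of simulated trials, against about 26% for the Week 16 change-versus-change correlation.
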